4.0 Enrollment/Randomization

The study will be conducted at the Mandell Center for MS (Mandell Center), which provides comprehensive care to persons with MS, thus allowing for easier recruitment of the intended patient population. As of December 31, 2019, 3,134 unique patients have been seen at the Mandell Center ([name], personal communication, January, 23, 2020). Similar to the general MS population³¹, our patient population has more women than men ([name], personal communication, November 16, 2017). Patients range from age 18 to 88 (mean: 50.23 years) and are, on average, moderately disabled, as measured by the Expanded Disability Status Scale (EDSS) (mean: 3.8; range: 0-8.5)³² ([name], personal communication, November 16, 2017).

Participants will be primarily recruited through the *Recruitment Pool for Studies at the Mandell Center for Multiple Sclerosis* (IRB# MSH-19-48), an ongoing project where PwMS opt-in to be contacted about research opportunities at the Mandell Center. To date, there are over 400 individuals who have agreed to be contacted about research studies being conducted at the Mandell Center. Potential participants will be contacted via email (with an IRB-approved recruitment letter) or via phone call. Recruitment flyers will also be posted in the Mandell

Center, made available to staff, and distributed to the community. All recruitment materials will list the inclusion criteria and contact information. Prior to enrollment in the study, potential participants will be screened over the phone for the inclusion criteria. As the study is primarily being conducted via telehealth, we plan to have participants have minimal on-site visits.

After completion of the baseline evaluations, participants will be randomized 1:1 into the treatment or control group, stratified by age and gender. A research assistance not involved in the data collection will be responsible for treatment allocation. This study will be single masked: different study personnel will be involved in the assessment and treatment portions of the study.

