At the baseline and post-treatment assessments, participants will be completing a battery of neuropsychological measures. These are protected, copyrighted measures that are being purchased under [name] license and will only be administered, scored, and interpreted by [name]. All of these measures are standard neuropsychological measures frequently used in routine neuropsychological assessments. The measures being given are noted in the attached document **TPMI Measure Checklist**. No diagnoses of cognitive impairment will be made after either assessments, as this study is not part of clinical care.

As these measures cannot be scanned and uploaded due to copyright restrictions and accordance with the American Psychological Association's ethics code, details are provided below on each measure:

Test of Premorbid Functioning (TOPF)⁴⁰: is a measure of premorbid functioning. The participant reads aloud a list of words, which increase in complexity. The participant will only complete this measure at baseline. If a participant completed the TOPF in another study (i.e., MSH-21-09), they will not repeat the TOPF in this study as their scores are expected to remain stable over time.

Memory for Intentions Test (MIST)^{28,29}: is an eight-task objective measure of PM. The participant is given eight tasks over the course of the test at differing times, to which they must give a response at either a designated time or after a certain cue. The tasks in the MIST are meant to mimic everyday activities (e.g., recalling what medications they take). The participants are given one additional task with a 24-hour delay, in which they would call a secure research line [contact]) and report how many hours of sleep they received the night before. The MIST will be given at baseline and post-treatment, and the total score will be used to calculate the preliminary effect size. To reduce learning effects, different versions of the MIST will be given at baseline and post-treatment.

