8.0 Statistical Considerations

For this project, we will be enrolling 36 participants (18 per arm). Fifteen participants has been previously identified as a sufficient sample size per treatment arm to calculate the sample size of a 90% powered main trial with a medium standardized difference⁴⁸. An additional six individuals (three per treatment arm) will be included to account for a 20% attrition rate during the course of the trial. This sample size is adequate to detect a large effect size with 76% power and 5% significance on a one-tailed independent t-test.

A flow diagram will be used to document recruitment, enrollment, and retention. Descriptive statistics will be used for adherence to treatment, and independent t-tests or Mann-Whitney U tests will be run for treatment credibility, expectancy, and satisfaction. For the preliminary efficacy calculations, an intent-to-treat approach will be used, with the expectation maximization (EM) approach to be used if justified by missing values analysis⁴⁹. Cohen's *d* effect size will be computed for the group difference and will be used to inform a definitive clinical trial.

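### Section 8.0 carries forward an uncorrected Cohen's d from 15 to 18 per arm; the small-sample (Hedges) correction would remove a 2.3% to 2.8% overstatement at no cost.

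*Combined protocol and SAP*

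**What the plan says.** Section 8.0 (Statistical Considerations) states that the Cohen's d "effect size will be computed for the group difference and will be used to inform a definitive clinical trial". Section 5.0, in its description of the Memory for Intentions Test (MIST), identifies the outcome: "the total score will be used to calculate the preliminary effect size". Aim 2 in section 2.0 calls the result a preliminary estimate for a future trial.

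On size, section 8.0 says "Fifteen participants has been previously identified as a sufficient sample size per treatment arm" for planning a main trial with 90% power and a medium standardized difference, and then "An additional six individuals (three per treatment arm) will be included to account for a 20% attrition rate". That makes 18 per arm enrolled and 15 per arm if the expected losses occur. Section 4.0 gives equal allocation: "participants will be randomized 1:1 into the treatment or control group".

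Neither section mentions a small-sample correction to d or a confidence interval for it. Section 8.0 does not say which SD standardizes the difference, or whether the difference is in post-treatment or change scores.

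**The concern.** Cohen's d divides the mean difference by an estimated SD. In small samples the expected value of 1/SD exceeds 1 over the true SD, so d lies too far from zero on average, whichever arm does better. The size of this bias depends only on the degrees of freedom and is known for normal data. Section 8.0 does not remove it.

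The standardized difference is the efficacy figure that the pilot hands to the next trial. Required sample size varies as 1 over the squared effect, so a proportional excess in d becomes roughly twice that proportion off the sample size read from it.

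**Working it through.** **Inputs from the documents.** 18 per arm enrolled, 15 per arm after planned attrition, 1:1 allocation, and a main trial with 90% power (sections 4.0 and 8.0).

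**Assumptions.** The documents give no numbers for a large or a medium effect, so I take 0.8 and 0.5. I also assume a pooled SD, normal data with equal variances, and two-sided 5% significance for the main trial.

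**The plan's own figure.** Section 8.0 says "This sample size is adequate to detect a large effect size" "with 76% power and 5% significance on a one-tailed independent t-test". With d = 0.8, 18 per arm and one-sided 5%, the noncentral t distribution gives 76.0%, so the figure reproduces. It applies to 18 per arm with no losses; at 15 per arm the same calculation gives 68.9%.

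**Bias factor.** With m = 2n - 2 degrees of freedom, J(m) = Gamma(m/2) / [sqrt(m/2) x Gamma((m-1)/2)], E[d] = true difference / J, and g = J x d. The usual approximation is J = 1 - 3/(4m - 1).

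| | 18 per arm | 15 per arm |
|---|---|---|
| m | 34 | 28 |
| J, exact | 0.97775 | 0.97293 |
| J, approximate | 1 - 3/135 = 0.97778 | 1 - 3/111 = 0.97297 |
| Excess of d, 1/J - 1 | 2.28% | 2.78% |
| Sample size ratio, J squared | 0.956 | 0.947 |
| Shortfall of n from d relative to n from g | 4.4% | 5.3% |

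**Bias against noise, true difference 0.5.**

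| | 18 per arm | 15 per arm |
|---|---|---|
| E[d] | 0.511 | 0.514 |
| Bias | 0.011 | 0.014 |
| SD of d | 0.350 | 0.386 |
| Bias as share of SD | 3.3% | 3.6% |
| RMSE of d | 0.350 | 0.386 |
| RMSE of g | 0.342 | 0.375 |

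Because J is below 1, g has a smaller variance than d as well as no bias. There is no trade-off.

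**What one pilot result implies** (noncentral t, 90% power, two-sided 5%):
- Observed d = 0.50: g = 0.489 (18 per arm) or 0.486 (15 per arm). The main trial moves from 86 per arm to 89 or 90.
- Observed d = 0.80: g = 0.782 or 0.778. The main trial moves from 34 per arm to 36.
- The 95% interval around an observed d of 0.50 is -0.17 to 1.16 (18 per arm) or -0.23 to 1.22 (15 per arm). The correction leaves that uncertainty essentially as it was.

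**Would planning on d undersize the trial on average?** The true difference is again 0.5.
- The median of d is 0.504 (18 per arm) or 0.505 (15 per arm), and d exceeds the truth in 50.4% or 50.5% of pilots. The median d implies 84 per arm against a target of 86. The median g is 0.493 or 0.491 and implies 88 or 89.
- Among estimates above 0.2, the mean sample size planned from d is about 101 (18 per arm) or 98 (15 per arm), against 84 for the true difference by the same normal approximation. The mean is above target because n depends on 1/d squared.
- Among estimates above 0.05, the chance that the planned trial has under 80% power is 44.9% with d and 43.3% with g (18 per arm), or 46.8% and 44.9% (15 per arm). Most of that risk is sampling error.

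**The case against.** The strongest reply is that this is a preference and not an error. Cohen's d is a standard descriptive measure, a reader can convert it to g from the reported sample sizes, and a bias of 3% to 4% of one SD is immaterial in a feasibility pilot. The first two parts of that stand, and they are why the point is minor. They do not count against the change, since g is better on both bias and RMSE and needs no further data.

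Two stronger readings are tempting, and neither is supported. A reader might infer that d will be entered directly in the main trial's sample-size formula. The documents say only that it will inform that trial and call it preliminary. A reader might also infer that the definitive trial would be undersized on average, by putting the mean of d (0.511 or 0.514) into the formula, which gives 82 or 81 per arm instead of 86. That does not follow: the sample size implied by the average d is not the average sample size, d is close to median-unbiased, and the mean planned n among usable estimates is already above target.

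It is also fair to say that J is exact only for normal data with equal variances. The documents give no distribution or SD for the MIST total, a score from eight tasks. Section 8.0 also allows values filled in by expectation maximization, which could understate the SD in a way that g does not repair. The claim is limited accordingly.

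**Conclusion.** The point holds as a minor one. Section 8.0 carries forward an estimator that overstates the true standardized difference by 2.3% (18 per arm) to 2.8% (15 per arm) in expectation, and a simple known correction is not applied. For a given pilot result the implied sample size is about 4% to 5% too small relative to the corrected value, which is 3 or 4 participants per arm at an observed d of 0.50.

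The percentages rest on a pooled SD, normality and equal variances. The sample sizes also rest on an assumed 90% power at two-sided 5%. The finding is about the reported estimate alone. It does not undermine the design, and it does not establish that the later trial would be too small.

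**What to change.** In section 8.0, replace Cohen's d with Hedges' g = J x d, J = 1 - 3/(4df - 1), on the MIST total score as the effect size reported and carried forward. State the degrees of freedom used. Between 28 and 34 the choice moves J only from 0.973 to 0.978, so it matters little, but it should be explicit if filled-in values are analysed.

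The cost is one changed term and one multiplication, with no extra participants, visits or data. The downside is that the reported effect becomes 2% to 3% less favourable. The correction does not replace a confidence interval for the effect, which would convey the much larger sampling uncertainty.

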The same randomized pilot trial will be used to compare the intervention ($n = 18$) to the control ($n = 18$).

Outcomes: The primary outcome will be objective PM abilities, as measured by the Memory for Intentions Test (MIST)^{28,29}, which will be used to generate a preliminary effect size estimate for a future trial. A secondary outcome will be subjective PM abilities, as measured by the Perceived Deficits Questionnaire (PDQ) subscale³⁰.

Hypothesis: Compared to the control group, participants in the treatment group will exhibit an improvement in their PM abilities. In addition, the treatment group will endorse fewer PM difficulties.

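### The primary efficacy outcome (MIST) has no named test, model or confidence interval, only a Cohen's d for an undefined group difference

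*Combined protocol and SAP*

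**What the plan says.** Section 2.0, Aim 2, makes MIST the primary efficacy outcome, "which will be used to generate a preliminary effect size estimate for a future trial". It states a directional between-group hypothesis, with the Perceived Deficits Questionnaire (PDQ) prospective memory subscale as a secondary outcome.

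Section 8.0 does three things:

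- **Size.** "we will be enrolling 36 participants (18 per arm"). Fifteen per arm is described as a "sufficient sample size per treatment arm to calculate the sample size of a 90% powered main trial with a medium standardized difference". Then: "An additional six individuals (three per treatment arm) will be included to account for a 20% attrition rate".
- **Power.** "This sample size is adequate to detect a large effect size with 76% power and 5% significance on a one-tailed independent t-test". No outcome is named.
- **Analysis.** Independent t-tests or Mann-Whitney U tests are assigned to treatment credibility, expectancy and satisfaction. For efficacy the section gives an intent-to-treat approach, expectation maximization (EM) if the missing-values analysis justifies it, and a Cohen's d whose "effect size will be computed for the group difference and will be used to inform a definitive clinical trial".

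Elsewhere, Section 5.0 has MIST given at baseline and post-treatment (week 6), with the total score used for the effect size. Section 4.0 stratifies randomization by age and gender.

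**The concern.** The main purpose of Aim 2 is an effect estimate, yet the plan does not say how that estimate is formed. The group difference could be in week-6 scores, in change from baseline, or in adjusted scores. The standardising SD could be the baseline, week-6 or change-score SD. These choices give different values of d from the same data, and nothing fixes the choice before the data are seen.

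No interval is promised, so the figure handed to the next trial carries no statement of its uncertainty, which at this size is large. The directional hypothesis has no inferential analysis assigned to it, and the power sentence is not tied to any analysis in the plan. The baseline MIST score and the stratification factors are collected or used in the design but have no stated place in the analysis.

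**Working it through.** **Inputs.** From Section 8.0: 18 per arm enrolled, 15 per arm needed, 20% attrition, one-tailed 5% t-test, 76% power, main trial at 90% power. Assumed, because the documents give no numbers: large is d = 0.8, medium is d = 0.5, and the main trial is tested two-sided at 5%.

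**1. The plan's own power figure.** For two independent means with n per arm, power is the probability that a noncentral t with 2n - 2 degrees of freedom and noncentrality d × √(n/2) exceeds the critical value.

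- 18 per arm: noncentrality 0.8 × √9 = 2.40, df = 34, one-sided critical value 1.691. Power = 76.0%, so the stated figure reproduces.
- 15 per arm: noncentrality 0.8 × √7.5 = 2.19, df = 28, critical value 1.701. Power = 68.9%.

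The 76% therefore needs all 36 participants analysed. The plan's allowance for attrition leaves 15 per arm (20% off 18 is 18 × 0.8 = 14.4).

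**2. Precision of d.** The exact 95% CI is found by inverting the noncentral t: t = d × √(n/2), find the noncentralities that place t at the 97.5th and 2.5th percentiles, and divide each by √(n/2).

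| Observed d | 15 per arm | 18 per arm |
|---|---|---|
| 0.5 | -0.23 to 1.22 | -0.17 to 1.16 |
| 0.8 | 0.05 to 1.54 | 0.11 to 1.47 |

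**3. What direct substitution would do.** This step assumes that the true d is 0.5 and that the observed d goes straight into the main-trial formula. Main-trial size for 90% power, two-sided 5%, by the t-test calculation:

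- d = 0.5: 86 per arm
- d = 0.8: 34 per arm

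At a true d of 0.5, 64 per arm gives 80% power, and about that size results from planning on d ≈ 0.577. Any larger observed d gives a main trial with true power below 80%. With 15 per arm in the pilot:

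- P(observed d > 0.577) = 0.42
- P(observed d ≥ 0.8) = 0.22; a 34-per-arm trial then has true power of about 53%
- P(observed d ≤ 0) = 0.085

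Errors also run the other way. In simulation, about 34% of pilots call for more than twice the needed number, counting those with d ≤ 0. With 18 per arm the share leading to under 80% power is about 41%, so the number analysed hardly matters.

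**4. Where a test is named.** In the analysis paragraph, tests are attached to the three participant ratings. MIST and the PDQ subscale have none.

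**The case against.** Several points on the other side stand.

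- **The statements in Section 8.0 do not contradict each other.** A reader might infer a conflict between "90% powered main trial with a medium standardized difference" and "This sample size is adequate to detect a large effect size". The first describes the later main trial and the second what this pilot could detect. A one-tailed t-test suits the directional hypothesis, and Cohen's d is its natural companion. What is missing is the link to MIST.
- **T-tests are in the analysis paragraph**, though only for the feasibility ratings.
- **Silence on baseline is not exclusion.** Aim 2 speaks of improvement and MIST is measured twice, so a change-score or adjusted d may be intended. The fair criticism is that it is undefined.
- **Direct substitution is not stated.** The plan calls the estimate preliminary and says it will inform the next trial, so the figures in step 3 describe a use that the documents leave open but do not commit to.
- **Intent-to-treat with EM may bring the analysed number to 18 per arm.** This barely narrows the interval.
- **This is a pilot with feasibility as Aim 1, and formal testing is optional.** That is fair, but a pilot whose efficacy product is an effect estimate still needs that estimate defined and given an interval.

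**Conclusion.** The point holds as an omission that is cheap to repair. The primary efficacy outcome has no named test, model or interval; its effect size is undefined as to score and SD; and the power sentence is tied to no outcome. The 76% is not an error. It is right for d = 0.8, one-tailed, with all 36 analysed, and about 69% at 15 per arm.

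The imprecision is substantial at either sample size: an observed d of 0.5 is compatible with values from below zero to about 1.2. The 42% chance of an underpowered main trial rests on four assumptions: true d = 0.5, direct substitution of the observed d, a main trial at two-sided 5% and 90% power, and 15 per arm analysed.

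A reader might infer that the definitive trial will be mis-sized, or that it must be sized on d = 0.5. The documents support neither. They give no sizing rule and no number for a medium difference. Checking whether 0.5 lies inside the pilot's interval would also decide little: even an observed d of zero has a 95% CI of about ±0.72 at 15 per arm.

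**What to change.** In Section 8.0:

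1. Analyse the week-6 MIST total by ANCOVA on arm, baseline MIST total, age and gender. Report the adjusted difference and a standardised d, each with a 95% CI, and state which SD standardises d. Other prespecified models would also close the gap; this one uses what the trial already collects and its stratification factors.
2. Use the same model for the PDQ prospective memory subscale, with its own baseline score.
3. State that the 76% refers to the unadjusted one-tailed MIST comparison at d = 0.8 with all 36 participants analysed.
4. State that the interval for d, not the point estimate alone, will be carried into planning of the definitive trial.

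The cost is a few sentences and a little more analysis, with no added participants, visits or measures. The drawback is a planning figure that looks visibly less precise.

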9.0 Privacy/Confidentiality Issues

There is a slight increase over minimal risk associated with this study. The measures being used to assess cognition are ones used by neuropsychologists as part of routine assessments, and the intervention materials mirror those used in cognitive rehabilitation or psychoeducation as part of clinical care. Minor inconvenience may occur during the completion of the assessments and intervention, which may be viewed as potentially frustrating, uncomfortable or distressing and time-consuming. If participants become distressed when discussing their cognition and its effects on their lives, they will be given the time in a private space to process their feelings. They will also have the option to discontinue answering any questions or the intervention. They will also be given a list of clinical resources if the participant expresses concern about their mood, level of anxiety, or cognition. These resources will be provided at the end of the research appointment, and will explain how participants can get a referral to services through their provider. Community resources will also be noted on this handout.

Only authorized persons will have access to the information gathered in this study. Patient names or other identifiers such as social security number, initials, birth date, etc., will not be used to identify electronic records. Identifiable information will only be used for contacting participants for follow-up appointments, compensation, and verification of information in the medical records. A code number will be used to code the questionnaires. The code number will not be based on any information that could be used to identify the participant (for example, social security number, initials, birth date, etc.). Data that are published will in no way identify the individual participants or disclose their identities.

